6.6.2 Management of Toxicities

The next cycle of treatment may begin on the scheduled Day 1 if:

- ANC is $\geq 1.000/\text{mm}^3$ (unless neutropenia is due to infiltration of bone marrow)
- Platelets $\geq 50000/\text{mm}^3$ (unless thrombocytopenia is due to infiltration of bone marrow, patient may have received transfusion) and absence of active bleeding
- No serious organ or other toxicity present.

If, based on medical judgment, the treating physician considers a change in laboratory parameter or AE not to be a study drug-related toxicity, but to represent a natural fluctuation in or progression of the underlying disease, then it is at the physician's discretion and assessment of the individual risk/benefit ratio to determine whether the patient should be dosed. The decision and rationale behind the decision should be documented in the source data.

If the above conditions are not met on Day 1 of a new cycle, the subject will be evaluated once every seven days and a new cycle will not be initiated until the toxicity has resolved as described above. Specific course of action for a given toxicity occurring in the course of the treatment cycle is described below.

If treatment needs to be interrupted for ≤ 28 days for the same study drug-related toxicity, the patient's treatment should continue, depending on the duration of treatment interruption, at the next protocol scheduled visit. No missed visits or doses of either drug should be made up.

If treatment with one study drug needs to be interrupted for >28 days for the same, persistent, drug-related toxicity, the study drug judged by the investigator to have caused the toxicity should be discontinued and the patient should continue to be dosed with the other study drug, as per protocol.

If treatment with both study drugs needs to be interrupted for >28 days for the same persistent study drug-related toxicity, judged by the investigator to be related to both study drugs (LEN and MOR00208), then the End of Treatment Visit will be performed and the patient will enter the follow-up phase (see [Section 5.3.1](#)).

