6.6.2.1 Haematological and Other Toxicities

Subjects will be evaluated for AEs at each visit with the NCI CTCAE v4.0 used as a guide for grading severity. The dose of study drug(s) for each patient will be interrupted and/or modified following toxicity as described below. Refer to [Table 2](#) and [Table 3](#) for instructions on dosing interruptions/modifications and [Table 4](#) for LEN dose reduction instructions.

Guidance on managing specific toxicities is summarised in [Table 2](#) and [Table 3](#).

Table 2 Haematological and Other Toxicities

Grade 3/4 thrombocytopenia judged to be related to study drugs	PLTs fall to <50000/ μ l	Interrupt MOR00208* and LEN dosing) Follow CBC every 7 days
	PLTs return to \geq 50000/ μ l	Provided all other criteria are fulfilled, resume dosing of MOR00208 and/or LEN. LEN should be administered at the next lower dose level (Table 4)
Grade 3/4 neutropenia judged to be related to study drugs	ANC falls to <1000/ μ l for at least 7 days or ANC falls to <1000/ μ l with an associated body temperature \geq 38.5°C or ANC falls to <500/ μ l	Interrupt MOR00208* and LEN dosing Follow CBC every 7 days Growth factors (G-CSF) and antimicrobial prophylaxis is to be used, as per local guidelines
	ANC return to \geq 1000/ μ l	Provided all other criteria are fulfilled, resume dosing of MOR00208 and/or LEN. LEN should be administered at the next lower dose level (Table 4)
Other clinically significant toxicities judged to be related to study drugs	Grade 3/4	Interrupt the administration of the study drug(s)* to which the toxicity is judged to be related to.
	Toxicities resolve to grade \leq 2	Provided all other criteria are fulfilled, resume dosing of study drug(s). LEN should be administered at the next lower dose level (Table 4)

Abbreviations: ANC=absolute neutrophil count; CBC=complete blood count; G-CSF=granulocyte colony-stimulating factor; LEN=lenalidomide; PLT=platelets.

*If, based on medical judgment, the treating physician considers a laboratory parameter change or AE not to be a study drug-related toxicity, but to represent a natural fluctuation in or progression of the underlying disease, then it is at the physician's discretion and assessment of the individual risk/benefit ratio to determine whether the patient should be dosed. The decision and rationale behind the decision should be documented in the source data.

Table 3 Other Toxicities Judged to be Related to LEN

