7 VISIT ASSESSMENTS AND PROCEDURES

7.1 Visit Schedule

[Table 5](#) lists all of the assessments, and indicates with an “X” the visits at which these assessments are performed. All data obtained from these assessments must be supported in the patient's source documentation.

Table 5 Schedule of Assessments
Schedule: Screening and Cycles 1–3

Evaluation or Procedure	Screening Period	Treatment Period												
	Screening ≤28 Days prior to D1	Cycle 1 (28 days)					Cycle 2 (28 days)				Cycle 3 (28 days)			
Day	Screen	D1	D4	D8 ±1 day	D15 ±1 day	D22 ±1 day	D1 ±1 day	D8 ±1 day	D15 ±1 day	D22 ±1 day	D1 ±1 day	D8 ±1 day	D15 ±1 day	D22 ±1 day
Informed consent	X													
Inclusion/exclusion criteria	X	X ¹												
Demography	X													
Medical history	X													
Disease staging/Ann Arbor	X													
Disease risk assessment (IPI)	X													
Previous/concomitant medication	X	X	X	X	X	X	X	X	X	X	X	X	X	X
Full physical examination (Limited physical examination - L)	X	L									L			
ECOG performance status	X	X ¹					X				X			
Body weight/height ²	X	X	X	X	X	X	X	X	X	X	X	X	X	X
B-symptoms	X	X					X				X			
Vital signs	X	X	X	X	X	X	X	X	X	X	X	X	X	X
12-lead resting ECG	X	X ³		X ³		X ³		X ³			X ³			
Urinalysis	X	X					X				X			
Pregnancy test (FCBP) ⁴	X	X ¹		X ¹	X ¹	X ¹	X ¹				X ¹			
Pregnancy and risks counselling	X	X					X				X			
“Emergency laboratory” ⁵		X	X	X	X	X	X	X	X	X	X	X	X	X
Central laboratory blood sampling ¹	X	X					X				X			
Serology Hepatitis B		X ¹⁶					X ¹⁶				X ¹⁶			
Serology Hepatitis C	X													
B-, T- and NK cell flow cytometry (blood) ¹		X		X		X	X							
Anti-MOR00208 antibodies		X ¹									X ¹			
Optional FcγR polymorphism (mucosal cheek swab)		X												
ADCC and CD16 assessment (blood)		X ¹												

Evaluation or Procedure	Screening Period	Treatment Period													
		Cycle 1 (28 days)					Cycle 2 (28 days)					Cycle 3 (28 days)			
Day	Screen	D1	D4	D8 ±1 day	D15 ±1 day	D22 ±1 day	D1 ±1 day	D8 ±1 day	D15 ±1 day	D22 ±1 day	D1 ±1 day	D8 ±1 day	D15 ±1 day	D22 ±1 day	
Disease and disease response assessment (CT/PET or PET/MRI)	X														
CT or MRI scan for tumour measurement and disease assessment (local)												X			
Central pathology review and correlative studies involving tissue samples	X														
Bone marrow aspiration & biopsy	X													X ⁷	
MOR00208 administration		X	X	X	X	X	X	X	X	X	X	X	X	X	X
LEN tablets allocation		X					X					X			
(S)AE assessment	X	X	X	X	X	X	X	X	X	X	X	X	X	X	X

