7.2.13.1 Safety and Haematology Laboratory Testing

Clinical laboratory tests will be performed according to [Table 6](#). During the course of the study, local ("emergency") and central laboratories will be used.

Central laboratory results are required for determining patient eligibility for study enrolment and will be used in the primary statistical analysis of the study results. Note: for eligibility confirmation prior to study drug administration at Cycle 1 Day 1, local laboratory results should be used. During the course of the study, all scheduled central laboratory results should be reviewed as soon as possible after Day 1 of each cycle.

During screening, it is permitted to repeat on a **single occasion** the central laboratory assessment of serum chemistry and haematology parameters due to the variability of the parameters and their dependence on multitude of factors (e.g., hydration, muscle mass). This is, provided no safety concerns arise and that such laboratory results might have been caused by a transient, medically plausible event, which resolved spontaneously or as result of a medical intervention in the meantime (e.g., dehydration, vomiting, imaging procedure with a contrast). This procedure and the rationale behind it must be explicitly documented in source data. Such repeated assessment (once only) of the concerned parameters will not be counted as "re-screening" for that patient.

Local ("emergency") laboratory results will be used for treatment or clinically related decisions, or for the immediate safety needs of a study patient. "Emergency laboratory" (local) results should be reviewed as soon as possible after their receipt and before dosing so that the administration of the investigational medicinal product (IMP) may be adjusted or interrupted if necessary.

The signed and interpreted laboratory results (both local and central) will be kept in the patient's source documentation. The laboratory results should be reviewed, dated and signed in a timely manner by the investigator. Any clinically significant discrepancies will be evaluated on a case-by-case basis. All blood samples will be processed and handled according to standard laboratory procedures. The time of blood collection should be documented in the source data.

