If an abnormal laboratory value of grade 4 or an abnormal laboratory value judged to be clinically significant that was not present at baseline, is not reported as an AE, then the investigator should clearly document the rationale for not doing so in the source documentation.

Any abnormal laboratory findings (identified either through local or central laboratory analysis) that constitute an AE should be reported as such and should be followed up until the outcome is known. Also, additional diagnostic tests may be indicated to determine a more precise diagnosis of the patient's condition (e.g., ordering a white blood cell (WBC) differential count to help characterise a high or low WBC count, or ordering a determination of red blood cell (RBC) indices to help characterise a low haematocrit).

Central laboratory tests will be performed only until Cycle 24 for each patient, as applicable.

Table 6 Laboratory Evaluations

Evaluation	Analysis
“Emergency laboratory”¹ (EDTA blood and serum sample)	Serum creatinine, haemoglobin, WBCs, WBC differential, platelets, sodium, potassium, AST, ALT, total bilirubin
Haematology (EDTA blood)	WBC with differential count, haematocrit, haemoglobin, mean corpuscular volume, mean corpuscular haemoglobin concentration, platelet count, RBC count, lymphocytes, monocytes, neutrophils, band neutrophils, eosinophils, basophils At screening: will include a peripheral blood smear Erythrocyte sedimentation rate kit from central lab will be used, however, the test as such has to be performed locally at the site.
Serum chemistry (serum sample)	ALT, total albumin, alkaline phosphatase, amylase, AST, bicarbonate, bilirubin (total), urea, total calcium, chloride, creatinine, creatinine kinase, GGT, glucose, LDH, lipase, phosphate, potassium, protein (total), sodium, uric acid, magnesium, β_2 -microglobulin, C-reactive protein
Coagulation parameters (sodium citrate blood)	Activated partial thromboplastin time, prothrombin time, international normalisation ratio, immunoglobulin concentrations (IgG, IgM, IgA)
Serology parameters (serum sample)	Hepatitis B: HbsAg, anti-Hbc and anti-HBs. HBV-DNA if anti-Hbc positive (until Cycle 24), Hepatitis C: HCV antibody (HCV RNA quantification if anti-HCV-positive)
Pregnancy test (serum sample)	β -HCG serum, females of childbearing potential only

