13.5 Laboratory data

13.5.1 Laboratory variables

Laboratory parameters measured in the central laboratory can be separated into

- Blood parameters (haematology, serum chemistry, coagulation).
- Urine parameters (urinalysis).

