13.5.3 Laboratory analysis

Laboratory data that are continuous in nature but are less than the lower limit of quantitation or above the upper limit of quantitation will be imputed. The limit of quantitation will be used for calculation of descriptive statistics if the data is reported in the form of " $\leq x$ " or " $< x$ " or " $\geq x$ " (x is considered as the limit of quantitation).

The following analysis on laboratory parameters will be performed:

- i. Laboratory parameters will be summarized. Descriptive summaries of actual (absolute) values and change-from-baseline values will be presented for haematology and serum chemistry for the SAF by visit. SI units will be used in the generation of these descriptive summaries. The assessment of categorical urinalysis variables will be tabulated by time point for each categorical urine parameter.
- ii. Abnormal values will be flagged in the listings (SAF population) to indicate whether the value is below or above the reference range and whether the investigator assessed the abnormal value as clinically significant. A clinically significant result can be commented with "Adverse Event", "Due to primary disease", "Pre-existing condition" or free text.
- iii. The assessment of the clinical significance of laboratory variables will be tabulated by time point for each clinical laboratory analyte.
- iv. For each laboratory parameter, shifts in assessments from baseline to worst-post baseline will be presented.
- v. If NCI-CTCAE grades are available for a clinical laboratory analyte, they will be derived according to NCI CTCAE, Version 4.03, and used to present additional frequency and shift tables based on NCI-CTCAE grades.

The following summary will be produced for the laboratory data (by laboratory parameter):

-
- Number (%) of patients with worst post-baseline CTCAE grade (regardless of the baseline status). Each patient will be counted only for the worst grade observed on-treatment
 - Shift tables to compare baseline to the worst post-baseline value will be produced for hematology and biochemistry laboratory parameters using:
 - CTCAE grades for laboratory parameters where CTCAE grades are defined.
 - The classifications relative to the laboratory reference ranges (low/normal/high) for laboratory parameters where CTCAE grades are not defined.
- vi. The following listing will be produced:

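### The worst-grade laboratory tables appear to rest on central samples, which are never scheduled mid-cycle, so neutrophil and platelet nadirs will be under-recorded

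*SAP*

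**What the plan says.** - **Data source.** SAP 13.5.1 opens with "Laboratory parameters measured in the central laboratory can be separated into" blood and urine parameters and names no other source. Protocol 7.2.13.1 says central results "will be used in the primary statistical analysis of the study results", whereas local "laboratory results will be used for treatment or clinically related decisions, or for the immediate safety needs of a study patient".
- **Output.** SAP 13.5.3 tabulates the worst post-baseline CTCAE grade ("Each patient will be counted only for the worst grade observed on-treatment") and shifts from baseline to the worst post-baseline value. Under SAP 6.8 the on-treatment period runs to 30 days after the last dose.
- **Central sampling.** In protocol Table 5, the row "Central laboratory blood sampling" is marked at screening, pre-dose on Day 1 of each cycle, and at the Unscheduled and EOT visits. Protocol 7.2.13.1 adds: "Central laboratory tests will be performed only until Cycle 24 for each patient, as applicable". Under 7.2.2, an EOT visit from Cycle 25 uses the local laboratory.
- **Local sampling.** The emergency panel, which includes the WBC differential and platelets (Table 6), is taken at every dosing visit.
- **Cycle start.** Protocol 6.6.2: "The next cycle of treatment may begin on the scheduled Day 1 if" ANC is at least 1000/mm³, platelets are at least 50000/mm³ and no serious toxicity is present. Marrow infiltration is exempt, platelets may have been transfused, and changes judged unrelated to study drug are left to the physician. Table 2 uses the same two limits, for example in its row "Grade 3/4 neutropenia judged to be related to study drugs".

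**The concern.** A worst-grade table is meant to show the depth of toxicity, so it needs samples taken when counts are likely to be lowest. The sampling days that the SAP appears to use are close to the opposite. Lenalidomide is taken on Days 1–21, so a Day 1 sample follows seven days without it. It is also taken on the day when low counts are a reason not to start the cycle. The counts taken between cycle starts, which drive mid-cycle interruptions, sit in the local panel.

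Neutropenia and thrombocytopenia are listed risks of MOR00208 (protocol 1.4.2) and prominent lenalidomide toxicities. One cited study of lenalidomide with rituximab reports grade 3/4 rates of 53% and 33% (protocol 1.3.3). At stake is a laboratory safety summary that understates cytopenia depth under a label saying it shows the worst grade, and that will not match interruptions made on local counts. The primary endpoint is not affected.

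**Working it through.** The plan gives no figure on this point to reproduce. Two checks apply.

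**1. Scheduled haematology draws (protocol Table 5)**

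Local: Cycle 1 on Days 1, 4, 8, 15, 22 (5); Cycles 2 and 3 on Days 1, 8, 15, 22 (4 each); Cycles 4–12 on Days 1 and 15 (2 each). Central: Day 1 of each cycle.

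- Local, Cycles 1–12: 5 + 4 + 4 + 9 × 2 = 31. Without the Cycle 1 Day 1 baseline: 30.
- Central, Cycles 1–12: 12. Without baseline: 11, all on Day 1.
- Mid-cycle: 31 − 12 = 19 (10 in Cycles 1–3, 9 in Cycles 4–12), all local only.
- To Cycle 24: local 31 + 12 × 2 = 55, so 54 post-baseline; central 24, so 23 post-baseline.
- From Cycle 25: no central results.

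Unscheduled and EOT central samples come on top of these counts.

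**2. How much a Day 1 schedule could miss**

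The documents do not give the duration or timing of cytopenias, so the following are assumptions. There is one below-limit episode in a cycle. Its onset is uniform over Days 2–28 (27 possible days) or Days 8–28 (21 possible days). It lasts d days. The next Day 1 is counted as Day 29. Visit windows and the Cycle 1 Day 4 draw are ignored.

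If central blood is drawn on the scheduled Day 1 even when the cycle cannot start, an episode is seen when onset ≤ 29 < onset + d. That is (d − 1)/27 or (d − 1)/21:

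- d = 3: 2/27 = 7%; 2/21 = 10%
- d = 7: 6/27 = 22%; 6/21 = 29%
- d = 14: 13/27 = 48%; 13/21 = 62%

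The same count with local draws on Days 8, 15, 22 and 29 (Cycles 1–3) or Days 15 and 29 (Cycles 4–12) gives:

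| Episode length | Central Day 1 | Local, Cycles 1–3 | Local, Cycles 4–12 |
|---|---|---|---|
| 3 days | 7–10% | 41–43% | 19–24% |
| 7 days | 22–29% | 100% | 48–62% |
| 14 days | 48–62% | 100% | 100% |

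If central blood is drawn only on the day a cycle actually starts, scheduled central capture is about zero, apart from the exceptions in 6.6.2 and differences between local and central readings.

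These are per-episode figures, while the SAP table counts patients. With three independent 7-day episodes, central capture per patient would be 1 − (1 − 6/27)³ = 53% to 1 − (1 − 6/21)³ = 64%.

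**The case against.** The strongest reply has four parts.

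- **Central-only is an inference.** SAP 13.5.1 classifies central parameters without excluding local ones. SAP 13.5.2 has a grading rule for a local laboratory range, and SAP 14.5 promises to list or tabulate other eCRF data. This stands, but the SAP does not include local data in these tables either, and protocol 7.2.13.1 points to central. The source has to be stated.
- **The cycle-start check governs dosing, not sampling.** A reader might infer that grade 3/4 values are removed from the tables by design. The documents do not support that. Nothing says the central sample is skipped when the check fails, and the check has exceptions. The certain loss is the absence of mid-cycle central draws; any further loss from the check is open.
- **Some central samples are outside the check.** EOT and Unscheduled Visit samples are not tied to it, and those within 30 days of the last dose count as on-treatment. Some severe cytopenias could be seen there. These samples do not replace the 19 mid-cycle draws.
- **Adverse event tables cover cytopenias.** Protocol 7.2.13.1 requires findings from either laboratory that constitute an AE to be reported. The SAP tabulates TEAEs of grade 3 or higher (10.7) and the time to onset and duration of neutropenia and thrombocytopenia (16.3.2, 16.5.2, 20.13). So a reader would not necessarily conclude that the combination is less myelosuppressive than it is. But AE reporting depends on investigator judgement: even a new grade 4 value may go unreported if the reason is documented in source. The laboratory tables are the natural check on that judgement.

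**Conclusion.** The point holds as a defect in source definition and labelling. Read as written, the plan builds worst-grade and shift tables from 11 scheduled post-baseline central draws in Cycles 1–12, all on Day 1. It leaves out 19 mid-cycle local draws and has no central result from Cycle 25. For ANC and platelets the direction is understatement.

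The size cannot be fixed from the documents. Under the assumptions above, central capture per episode runs from about zero to 62%, depending on episode length and on whether a failed Day 1 is sampled. A reader might be tempted to apply a capture fraction to the lenalidomide–rituximab rates and quote a reported percentage for this trial. That would combine another regimen's rates with an unsourced fraction. The numeric check covers ANC and platelets only, so the argument is weaker for the other analytes.

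**What to change.** In SAP 13.5.1 and 13.5.3, state which results feed each table. Derive the worst post-baseline grade and the shift tables, at least for ANC and platelets, from all on-treatment results in the study database: central, local and unscheduled. Keep central-only data for the by-visit descriptive statistics.

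If local values are not in the database, retitle these tables as central Day 1/EOT values. Add a footnote that they show neither mid-cycle nadirs nor any result from Cycle 25 onwards, and refer to the AE tables for cytopenia frequency.

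The cost is SAP wording and some programming. Local reference ranges would be mixed, which matters little for grade 3/4 ANC and platelets because the limits are absolute counts. The reported grade 3/4 rates may look less favourable. Back-entry of all local values from source is not asked for: for 80 patients, 31 visits and 10 panel items it could reach 80 × 31 × 10 = 24,800 values, an upper bound if every patient completed 12 cycles. Retitling costs almost nothing.

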13.5.2 Grading of laboratory data

Laboratory data grades of severity will be derived according to the Common Terminology Criteria for Adverse Events (CTCAE) v4.03. A severity grade of 0 will be assigned when the value is within normal limits. In the case a local laboratory normal range overlaps into the higher (i.e. non-zero) CTCAE grade, the CTCAE grade will be taken. Lab values having hyper or hypo shifts will be classified as a particular CTCAE grade irrespective of the shift direction (no differentiation between CTCAE grades resulting from increased or decreased lab values). The laboratory values for which CTCAE grades are defined for only one direction of deviation (e.g., platelet count) will be assigned grade 0 in case a laboratory value is outside the reference range, but in a direction for which CTCAE grading is not defined.

Laboratory test results will also be shown by the low/normal/high classifications based on laboratory normal ranges.

For duplicate laboratory measurements taken at the last assessment date on or before the start date of study treatment, the value of lower CTCAE grade will be considered as the baseline value.

For non-gradable labs with duplicate laboratory measurements taken at the last assessment date on or before the start date of study treatment:

- If both within normal range: take average value.
- If one within normal range and the other outside: take the one within normal range.
- If both outside normal range: take the one closest to the normal range.

Laboratory values with missing units or normal range may not be able to be graded or included in laboratory tables.

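### The CTCAE laboratory tables pool high and low abnormalities, so for analytes graded both ways no specified summary table shows severity and direction together

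*SAP*

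**What the plan says.** SAP 13.5.2 sets the grading rule: "Lab values having hyper or hypo shifts will be classified as a particular CTCAE grade irrespective of the shift direction", with "no differentiation between CTCAE grades resulting from increased or decreased lab values" added in parentheses. Values within normal limits get grade 0. The same section treats analytes graded in one direction only as a separate case, with platelet count as its example: for these, an abnormal value on the ungraded side is set to grade 0. The merging rule therefore bites only on analytes graded in both directions.

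SAP 13.5.3 then uses the grade in two outputs.

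- **Worst post-baseline frequency table:** "Each patient will be counted only for the worst grade observed on-treatment".
- **Shift tables:** "Shift tables to compare baseline to the worst post-baseline value will be produced for hematology and biochemistry laboratory parameters using" one of two scales. The first is "CTCAE grades for laboratory parameters where CTCAE grades are defined". The second is "The classifications relative to the laboratory reference ranges (low/normal/high) for laboratory parameters where CTCAE grades are not defined".

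Two further statements bear on direction. SAP 13.5.2 adds: "Laboratory test results will also be shown by the low/normal/high classifications based on laboratory normal ranges". Item iv of SAP 13.5.3 promises a baseline-to-worst shift for every parameter but does not name the scale. Items ii and vi of SAP 13.5.3 provide listings that flag values below or above the reference range.

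**The concern.** An excess and a deficit of the same analyte are different toxicities, often with different causes. A table that reports one grade for both tells the reader how severe the abnormality was but not what it was. The trial is single-arm, so these tables describe laboratory toxicity with no comparator to help interpret them.

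Three things go wrong for an analyte graded both ways:

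1. Every graded abnormality is ambiguous. A patient in the cell for grade 0 at baseline and grade 3 at worst may have had either toxicity.
2. A patient who has both on treatment contributes one count, at the worse grade. The milder one leaves the frequency table.
3. A patient who swings from an excess to a deficit, or the reverse, is placed by the size of the two grades alone.

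The first two need no reversal, so they matter most in practice.

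**Working it through.** The plan states no figure to reproduce, and no power or error-rate calculation applies. The check is to follow the unsigned grade through each table.

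**Frequency table.** For one analyte, let H be the set of patients whose worst on-treatment excess is at or above a given grade, and L the same for a deficit. The number at or above that grade in the planned table is

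|H ∪ L| = |H| + |L| − |H ∩ L|.

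If this number is n, the number of patients with the deficit can be anything from 0 to n, and likewise for the excess. Neither incidence can be recovered from the table.

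**Shift table.** List every reversal of direction with grades 1 to 4 at baseline and at worst post-baseline. There are 2 directions × 4 baseline grades × 4 post-baseline grades = 32 cells. Under the unsigned rule:

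| Reading in the table | Condition | Grades 1–4 | Grades 3–4 only |
|---|---|---|---|
| No shift | grades equal | 2 × 4 = 8 | 2 × 2 = 4 |
| Worsening | post-baseline grade higher | 2 × 6 = 12 | 2 × 1 = 2 |
| Improvement | post-baseline grade lower | 2 × 6 = 12 | 2 × 1 = 2 |
| Total | | 32 | 8 |

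A grade 4 excess followed by a grade 3 deficit as the worst later value is one of the cells that read as improvement.

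**Same cells with direction-specific grades.** If values abnormal in the other direction are set to grade 0, a grade 3 excess that becomes a grade 3 deficit appears as 3 to 0 in the hyper table (assuming no excess after baseline) and as 0 to 3 in the hypo table. On a signed scale, 0 of the 32 reversals fall on the diagonal.

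These are counts of possible table cells. They are not expected numbers of patients.

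**Which analytes.** The laboratory table in Protocol 7.2.13.1 (Table 6) includes sodium, potassium, total calcium, magnesium and glucose. Neither document says which analytes are graded both ways, so these are candidates to check against CTCAE v4.03, not a documented count.

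**Where severity and direction are shown:**

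| Output | Severity | Direction | Incidence |
|---|---|---|---|
| Worst-grade table | yes | no | yes |
| CTCAE shift table | yes | no | yes |
| Low/normal/high display, if produced for graded analytes | no | yes | not stated |
| By-visit values and changes | no grade | yes, at group level | no |
| Listings | yes | yes | no |

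No specified laboratory summary table gives severity and direction together.

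**The case against.** The strongest reply is that SAP 13.5 can be read as already giving directional shifts. The low/normal/high sentence in 13.5.2 is not limited to analytes without CTCAE grades. Item iv of 13.5.3 covers every parameter, and item v calls the CTCAE tables additional. Together these suggest a low/normal/high shift for all analytes, supplemented by a CTCAE shift. Against that, the explicit shift-table bullets give low/normal/high only to analytes without CTCAE grades. The scale of item iv is therefore ambiguous. Even on the generous reading, one table would show direction without severity and the other severity without direction.

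The second reply is that clinically important events reach the adverse event tables. Protocol 7.2.13.1 asks for a documented reason when a new grade 4 or clinically significant value is not reported as an adverse event, and SAP 10.7.3 tabulates events by preferred term and grade. This stands and limits the harm. It depends on the investigator's judgement for values below grade 4, however, and so does not replace a laboratory table built from all measured values.

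A reader might also infer three stronger things, none of which the documents support:

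- **Reversals are missed entirely.** They are not: the listings show grade and direction for each value.
- **Any swing between a high-grade excess and a high-grade deficit shows as no shift.** This holds only at equal grades, 4 of the 8 cells at grades 3 and 4.
- **At least five analytes are affected.** The documents do not say which analytes CTCAE grades both ways.

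Nothing in the documents suggests that high-grade reversals will be common in about 80 patients.

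**Conclusion.** The point holds as a gap in safety presentation. For analytes graded in both directions, the worst-grade table and the CTCAE shift tables pool opposite toxicities, and the incidence of either cannot be read from them. Equal-grade reversals read as no shift, and unequal ones as worsening or improvement without direction.

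The information is not lost from the data, and direction can be traced in the listings, the by-visit summaries and the adverse event tables. No conclusion on efficacy, sample size or error rates changes. The conclusion assumes that at least one measured analyte is graded both ways under CTCAE v4.03, which the SAP's own rule presupposes. How many patients are affected cannot be estimated from the documents. The case for acting rests on a stated rule that obscures laboratory toxicity and is very cheap to change.

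**What to change.** In SAP 13.5.2, replace the direction-blind rule for analytes that CTCAE v4.03 grades both ways, and name those analytes. Derive a hypo grade and a hyper grade for each, with a value abnormal in the other direction set to grade 0. The SAP already uses this convention for analytes graded one way.

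In SAP 13.5.3, present the worst post-baseline frequency table and the shift table separately for each direction, taking the worst value within that direction. State the scale of the item iv shift, and say which output carries the low/normal/high display.

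The cost is some programming and a few extra table rows. The listings already require each value to be flagged as below or above range, so no new data are needed.
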